Hypothesis 1b: Connections within the decision-making network will exhibit both anatomical (DTI and VBM) and functional disruption in NAUD, AUD and NUD groups relative to CS. We predict that alcohol and nicotine use are associated with greater cortical (cingulate and prefrontal cortex) thinning and decreased white matter integrity in superior and inferior longitudinal fasciculi and rostral trans-callosal fibers.

Expected Outcomes and Alternatives: Our hypothesis would be supported by finding reduced FA in the tracts that connect (directly or indirectly) regions between which there is decreased functional connectivity. The combined anatomical/functional connectivity analysis we propose has not been previously used in addicted populations, although a similar approach yielded informative data in schizophrenia (Kubicki et al., 2009; Skudlarski et al., 2010). We will perform regular QA to ensure that the quality of the data is high. This will allow us to make any modifications to our protocol and, if necessary, recruit additional subjects. We will consult regularly

with [name] about anatomical and functional connectivity.

SA 2: Develop a machine learning model that integrates behavioral, task and resting state functional activation, volumetric data and structural connectivity that a) differentiates the four groups and b) predicts treatment outcome at 3 months.

C6. Machine Learning: SVM Approach: The SVM algorithm [LIBSVM, (Chang and Lin, 2011)] calculates a hyper-surface that separates the groups. This process requires selection of a kernel function that describes the projection of the feature vector (e.g., AMR in *a priori* ROIs, **Error! Reference source not found.**, **Table 3**) associated with each individual into multidimensional space (e.g., a simple scalar product for a

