linear kernel) and requires selection of parameters characteristic of each kernel and a constant, C, that characterizes the error penalty. Our approach (schematic in **Figure 3**) to a machine learning model (Schoelkopf and Smola, 2001) closely follows the method of Ding et al. (2015). **Feature extraction:** The first step in this analysis is extraction of features from the functional, resting state, volumetric and white matter connectivity datasets that will be used in the Support Vector Machine. We plan an ROI based analysis (e.g., see **Table 3**). This set of regions will be adjusted and expanded after preliminary analysis of functional and anatomical measures that statistically separate the four groups. Specifically, we use the following suitably scaled features: 1) average cortical density in the ROIs extracted from VBM; 2), average FA in white matter tracts connecting the ROIs (from atlas tract-based spatial statistics (TBSS)), 3) rsMRI connectivity correlation matrices between ROIs, 4) regional parametric regressor means and 5) clinical and demographic variables.

C6a. Classification of AUD, NUD, NAUD and CS (SA2a): The method can be extended to multigroup classification [see, e.g., (Hsu and Lin, 2002; Forkert et al., 2015); (Lajnef et al., 2015), albeit with somewhat greater complexity. LIBSVM uses the “one-against-one” method, which essentially approaches the problem as multiple binary classification problems (there are 6 binary classifiers for 4 groups). We will use the same set of features as above, but the rank order of features may differ.

C6b. Three-month outcome (SA2b): For the outcome predictor, cigarettes per day and pack-years will be added as a feature. We cross-validate the model using a bootstrapping procedure (**Figure 3**). We plan on testing a range of kernels such as the linear, polynomial, radial, and sigmoid kernels. The data will be divided into a training set and a test set (70%/30% split, stratified by relapse status). For each kernel type, we will use 10-fold cross-validation within the training set to determine optimal parameters amongst a wide range of

values. The SVM’s with the optimal parameters will then be applied to the test set. This procedure will be simulated 10,000 times, from which an optimal kernel and corresponding parameters will be selected.

C6c. Expected Outcomes and Alternatives:

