We will examine the performance of the SVM classifier by calculating sensitivity, specificity and balanced accuracy. Sensitivity = $TP/(TP + FN)$, Specificity = $(TN/(TN+FP))$ and Balanced Accuracy = $(1/2)(TP/(TP+FN) + TN/(TN+FP))$, where TP is true positive, FP is false positive, FN is false negative, and TN is true negative. The model will be especially useful if balanced accuracy reaches ~70%. If accuracy is below this number, we will investigate refinements or alternatives to our model building techniques. If SVM methods still prove intractable, we are currently developing alternative methods including a random forest approach and multivariate distance matrix regression [MDMR (Zapala and Schork, 2012)]. These methods have

$$\begin{aligned}
 1.1 \quad V_p &= \frac{M}{(1+kt)} \quad V_p = \frac{M}{(1+h\theta)} \\
 1.2 \quad V_p &= \frac{M}{(1+kt)(1+h\theta)} \Rightarrow \frac{20}{M} = \frac{1}{(1+kt)(1+h\theta)} \\
 1.3 \quad V'_{uc} &= \frac{V_{uc}}{V_{tot}} = \frac{1}{1 \cdot 12 \cdot 3} \int_0^{12} \int_0^3 \frac{dt d\theta}{(1+kt)(1+h\theta)} = \\
 &= \int_0^{12} \frac{dt}{12(1+kt)} \int_0^3 \frac{d\theta}{3(1+h\theta)} = \frac{A_k}{12} \frac{A_h}{3} = A'_k A'_h
 \end{aligned}$$

Figure 2: Analysis of discounting tasks. V_p is the immediate value of the amount M , available after delay, t or odds against, θ = $(1-p)/p$, where p is the probability of receiving the reward.

V'_{uc} is the fractional volume under the discounting surface.

been used to classify individuals with addiction [(Squeglia et al., 2016), random forest] and ADHD [(Yang et al., 2016), MDMR].

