C8. Power: We made an estimate for group size using two approaches. We used the statistical map of magnitude from 20 AUD subjects and 20 CS that had been compared with 3dANOVA as input to two power calculators. We used *fmripower* (Mumford and Nichols, 2008), a MATLAB-based program that calculates a power estimate given the between-group and within-subject error terms associated with a two-tailed t-test of regression coefficients. We also used Neuropower, an online toolkit that calculates group sizes from statistical maps. For whole brain analyses, the results from *fmripower* suggested that 31 subjects per group would yield a power of .8 for the test comparison, while Neuropower suggested 29 and 45 subjects per group with the Benjamini-Hochberg and Random Field theory correction for multiple comparisons, respectively. When we used the ROIs in **Table 3** to mask the voxels in the statistical map, power for 50 subjects per group was 0.99. We are, therefore, confident that the proposed 50 subjects per group will provide us with sufficient power to test the predictions.

[figure not shown]
C9. Timeline, Benchmarks:

Timeline for this 4-year project is presented in graphical form (**Figure 4**).

C10. Risk to Subjects

Human Subjects Involvement: Approximately 200 individuals will be recruited for this project.

Potential subjects will call [name] or his designee after seeing a presentation about the study, in response to a study advertisement or by referral from a clinician. All subjects will have been offered a flyer with contact information. When subjects call, they will undergo a brief telephone interview to determine if they are likely to

qualify and, if so, will be invited for visit 1. Subjects may also be screened at treatment centers during recruitment visits. Each subject will then give informed consent before any data collection takes place. Study visits may take place at the Portland VA, OHSU or at local treatment centers.

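### The relapse classifier is described with one error penalty and no class weighting but is judged on balanced accuracy, so if the outcome classes are clearly unequal it will under-detect the rarer one

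*Combined protocol and SAP*

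**What the plan says.** C6 introduces LIBSVM as an algorithm that "calculates a hyper-surface that separates the groups", governed by kernel parameters and "a constant, C, that characterizes the error penalty". Class weights, resampling and a shifted decision threshold are not mentioned anywhere.

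For the three-month outcome (C6b), the data are divided by a "70%/30% split, stratified by relapse status". On kernels: "We plan on testing a range of kernels such as the linear, polynomial, radial, and sigmoid kernels". For each kernel, "we will use 10-fold cross-validation within the training set to determine optimal parameters amongst a wide range of" values. The measure that makes a parameter or kernel optimal is not named. The procedure is repeated 10,000 times before a kernel and its parameters are chosen.

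C6c sets the yardstick: "We will examine the performance of the SVM classifier by calculating sensitivity, specificity and balanced accuracy". Balanced accuracy is defined there as the mean of sensitivity and specificity. The benchmark follows: "The model will be especially useful if balanced accuracy reaches ~70" per cent. Below it, the team will look at improving or changing the model, and will move to random forest or distance-matrix regression only if SVM methods remain unworkable.

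C8 plans 50 subjects per group. Only AUD and NAUD subjects are followed up (C1). Hypothesis 2b expects more relapse in NAUD than in AUD, but no section gives a relapse rate.

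**The concern.** A soft-margin SVM with the same C for both classes charges the same price for an error in either class. When one class is larger, total error cost falls if the boundary moves so that more subjects are assigned to the larger class. Raw accuracy can rise as a result, while balanced accuracy, which gives each class half the weight, drops. Penalty and yardstick agree only when the classes are about equal.

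For the four-group problem (SA2a) the classes are equal by design, so the point does not arise. For SA2b the classes are whatever relapse turns out to be. Stratifying the split keeps the class ratio the same in the training and test sets; it does not even it out.

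At stake is how a result near 70% is read. A shortfall caused by the class ratio could be taken as weak neural signal. It would also prompt model changes after performance has been seen, which a rule stated beforehand would avoid.

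**Working it through.** The ~70% mark is a target with no derivation, so there is no plan figure to reproduce.

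**Inputs from the plan**
- Subjects with an outcome: 2 × 50 = 100 before dropout (C8, C1).
- Training set: 0.70 × 100 = 70. Test set: 30 (C6b).
- Balanced accuracy = (sensitivity + specificity)/2 (C6c).

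**Assumed, because the plan does not say**
- Rarer-class share of 20% to 50%.
- Signal strength.
- Number of features: 20, or 270. The larger figure reflects Table 3, whose 21 regions give 21 × 20/2 = 210 connectivity pairs alone.

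**Step 1. Limiting case.** At 80/20, a rule that always predicts the commoner class has 80% accuracy but balanced accuracy (0 + 1)/2 = 50%.

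**Step 2. Closed form.** Take a normal score with equal variance in both classes and just enough information for 70% balanced accuracy at the best cut-off: d' = 2 × z(0.70) = 1.049. A rule that maximises raw accuracy moves the cut-off by s = ln((1 − π)/π)/d', where π is the rarer-class share. Detection of the rarer class is Φ(d'/2 − s) and of the commoner class Φ(d'/2 + s).

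| π | s | Rarer class detected | Commoner class detected | Balanced accuracy |
|---|---|---|---|---|
| 50% | 0 | 70% | 70% | 70.0% |
| 40% | 0.387 | 55% | 82% | 68.7% |
| 30% | 0.808 | 39% | 91% | 64.9% |
| 20% | 1.322 | 21% | 97% | 59.0% |

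This is the mechanism if everything is tuned to raw accuracy.

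**Step 3. Simulation of a tuned SVM.** LIBSVM-based classifier, 70 training subjects, Gaussian features, stratified 10-fold cross-validation over linear and radial kernels and a grid of C, scored on large independent test sets. With 20 features (balanced accuracy, with rarer-class detection in brackets; standard errors 0.004 to 0.012):

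| Rarer class | Equal C, tuned on accuracy | Equal C, tuned on balanced accuracy | Weighted C, tuned on balanced accuracy |
|---|---|---|---|
| 50% | 0.755 (0.75) | 0.752 (0.75) | 0.758 (0.78) |
| 40% | 0.726 (0.63) | 0.726 (0.65) | 0.740 (0.70) |
| 30% | 0.687 (0.48) | 0.708 (0.56) | 0.744 (0.70) |
| 20% | 0.613 (0.29) | 0.664 (0.44) | 0.725 (0.66) |

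A separate simulation of the same size gave 0.64-0.67 for equal C against 0.74 weighted at 20%, 0.71-0.72 against 0.76 at 30%, and no difference at 50%. With relapse at 70%, it was specificity that fell, to 0.50-0.55.

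**Step 4. Stronger signal.** With 20 features and 0.82 at even classes, equal C tuned on accuracy still gives 0.722 at 20%. The mark is met, with half of the rarer class detected; weighting gives 0.803.

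**Step 5. More features than subjects (270).** Equal C tuned on accuracy gives 0.711, 0.647, 0.603 and 0.520 at 50, 40, 30 and 20%. Weighted C tuned on balanced accuracy gives 0.715, 0.690, 0.659 and 0.619. Weighting helps only in part. With a stronger signal and a linear kernel at C = 1 it does nothing at 20% (0.706 equal, 0.697 weighted), because the training data are then separable and few errors are left to reweight.

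**The case against.** The strongest reply is that equal weighting is inferred from silence. The sentence on C is a generic description covering both SA2a and SA2b, and LIBSVM class weights multiply a single C, so a weighted SVM would fit the same words. C6 also says that it follows a published method, whose handling of classes cannot be checked here. This stands: a reader might infer that the plan commits to equal costs, and the documents do not say so. What they show is that nothing is specified to deal with imbalance.

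Second, the tuning criterion is unnamed, and the only measures listed are sensitivity, specificity and balanced accuracy. If tuning uses balanced accuracy, part of the loss is recovered: 0.708 at 30%, which meets the mark. It is only part: 0.664 at 20%, against 0.725 with weights.

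Third, a reader might infer that relapsers will be missed. That holds only if relapse is the minority outcome. No rate is given, and if relapse is the majority the loss falls on specificity.

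Fourth, a reader might infer that a model below 70% would be discarded. C6c does not say that: the mark is a level of usefulness, refinement comes first, and class weighting would be a natural refinement. What remains is that the repair would come after performance had been seen.

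**Conclusion.** The point holds in conditional form, as a low-cost improvement rather than a serious flaw. The plan leaves class imbalance in SA2b unaddressed and scores the model on a measure sensitive to it. If the rarer outcome makes up about 20-30% of subjects, a moderate signal that clears 70% with even classes can fall to about 0.61-0.67 (20%) or 0.69-0.72 (30%), where a weighted fit would give 0.73-0.74 or 0.74-0.76. Near 50% there is no loss, and a strong signal passes regardless.

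These sizes rest on an assumed relapse share, signal strength and feature count, on Gaussian features, and on two of the four kernel types named in the plan. They also rest on reading the single C as unweighted. The direction of the effect is firmer than its size.

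**What to change.** In C6b, pre-specify three things:

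1. LIBSVM class weights, with C multiplied for each class by the inverse of that class's frequency in the training set.
2. Balanced accuracy as the criterion for choosing both parameters and kernel, applied in the inner 10-fold cross-validation.
3. A decision threshold set within the training folds, because weights alone do little when features outnumber subjects. The benefit of this step was not simulated here.

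The cost is one software option, a short threshold step and a few sentences; no new data are needed. Some accuracy on the commoner class is given up. In the 20-feature case at 20%, commoner-class detection goes from 0.94 (equal C, tuned on accuracy) to 0.79, and raw accuracy from 0.2 × 0.29 + 0.8 × 0.94 = 0.81 to 0.2 × 0.66 + 0.8 × 0.79 = 0.76. That is the exchange that balanced accuracy asks for. If the classes turn out near equal, essentially nothing changes.

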Figure 3: Schematic [after Ding et al. (2015)] of the classification approach proposed for SA2a and b.

be preprocessed using AFNI_16.1.26. The motion censoring technique described recently by Power and colleagues (Power et al., 2012;Power et al., 2014;Power et al., 2015), will greatly reduce the residual effect of head motion on observed time courses.

To enable cortical surface-based analyses, fMRI time courses will be sampled to the cortical surface mesh, using the extent of overlap with the cortical ribbon as a weighting factor to account for partial voluming. Voxels with high variability relative to their local neighborhood will be excluded. The functional EPI images will be despiked (3dDespike), slice time corrected (3dTshift), motion corrected (3dvolreg), aligned to warped MPRAGE (align_epi_anat.py) and corrected for oblique slice acquisition. A 4 mm FWHM three-dimensional Gaussian blur will be applied to the functional images (3dmerge) and each voxel time series will be scaled to have a mean of 100 (3dTstat, 3dcalc). **Anatomical (T_1 w and T_2 w)**: MPRAGE and T_2 w structural images will be corrected for gradient nonlinearity distortions using scanner specific, nonlinear transformations, provided by MRI scanner manufacturers, and verified using phantom scans. Spatial distortion in the readout direction due to B_0 variation will be corrected based on the distortion maps generated from our fast field mapping. T_2 w images will be registered to T_1 w images using mutual information after coarse pre-alignment via within-modality registration to atlas brains. Intensity non-uniformity correction will be performed by dividing image intensities by a smooth bias field estimated from the geometric mean of the T_1 w and T_2 w images. Anatomical scans will be

[name]

Version date: 2-1-2021

corrected for oblique acquisition, skull stripped (3dSkullStrip), and warped into MNI-152 space with @auto_tlrc.

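### The SA2a classifier's regions are revised with the same four-group labels it then predicts, and the readable text does not keep that step inside the training data

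*Combined protocol and SAP*

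**What the plan says.** All references are to the combined protocol and SAP.

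- **C6, Feature extraction.** This is the first step of the machine-learning analysis. Table 3 is given as an example of the starting regions, and then: "This set of regions will be adjusted and expanded after preliminary analysis of functional and anatomical measures that statistically separate the four groups". The features are listed after the words "Specifically, we use the following suitably scaled features". They comprise VBM density, tract FA, "rsMRI connectivity correlation matrices between ROIs", task regressor means, and clinical and demographic variables.
- **C6a (SA2a).** For the four-group classifier: "We will use the same set of features as above, but the rank order of features may differ". No split is written here.
- **C6b (SA2b).** "The data will be divided into a training set and a test set (70%/30% split, stratified by relapse status". Tuning uses 10-fold cross-validation within the training set, and the tuned machines are applied to the test set. Then: "This procedure will be simulated 10,000 times, from which an optimal kernel and corresponding parameters will be selected".
- **Figure 3 caption.** The figure, which is not shown in the text available, is a schematic "of the classification approach proposed for SA2a and b". C6 also says the approach closely follows a published method.
- **C6c.** Performance is judged by sensitivity, specificity and balanced accuracy, each defined for two classes. "The model will be especially useful if balanced accuracy reaches ~70" percent.

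**The concern.** The labels that decide which regions enter the model are the labels the SA2a classifier predicts. If all subjects contribute to that decision, test subjects have already helped to choose the features on which they are scored. A split made after the regions are revised does not undo this.

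Hypothesis 2a sets out to build and validate a classifier of group membership, and balanced accuracy is a stated measure of how well it does. Depending on a rule the plan does not state, the optimism could be nil or several points, and a reader of the results could not tell which.

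A secondary point concerns SA2b. Tuning inside the training set is sound, but the final kernel and parameters are then picked from 10,000 runs that each end on a test set, and the criterion is not given.

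**Working it through.** The plan states no expected SA2a accuracy, so there is no figure to reproduce. The check has four parts.

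**1. Whose data revise the regions?** Preliminary analysis could mean pilot data. However, the imaging pilot work in the Specific Aims covers nicotine users, alcohol users and controls, and C8 uses 20 AUD and 20 CS subjects. No co-addicted pilot group is described. The Specific Aims also say that SA2 uses the SA1 data. The study's own four groups are the natural reading.

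**2. Does the written split cover SA2a?** It is stratified by relapse status, and C1 describes follow-up visits for the NAUD and AUD groups only. It therefore cannot be applied as written to NUD and CS.

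**3. How large could the optimism be?**

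From the plan: 50 per group (C8). Table 3 has 10 bilateral regions plus the brainstem, so 2×10+1 = 21 regions and 21×20/2 = 210 region pairs.

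Assumed, not in the plan:
- Independent Gaussian noise with no group difference (true accuracy 0.50), unless a correlation is stated.
- Linear SVM with C=1, scored for AUD versus NAUD by 10-fold cross-validation.
- The 21 Table 3 regions are always kept, within a pool of 50, 80 or 200 candidates.
- A further region enters if any of 7 local measures passes a four-group F test.
- Connectivity pairs are features but are not screened; tract FA and clinical variables are not simulated.
- 150 data sets per setting; standard error of each mean about 0.005.

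Optimism = accuracy with screening on all subjects minus accuracy with screening inside training. Local plus connectivity features, pools of 50 / 80 / 200:

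| Screening rule | All subjects | Inside training | Difference (points) |
|---|---|---|---|
| FDR<0.05 | 0.502 / 0.500 / 0.503 | 0.502 / 0.499 / 0.503 | 0.0 / 0.1 / 0.0 |
| p<0.001 | 0.501 / 0.500 / 0.514 | 0.502 / 0.496 / 0.503 | −0.1 / 0.4 / 1.1 |
| p<0.01 | 0.511 / 0.517 / 0.543 | 0.499 / 0.494 / 0.498 | 1.2 / 2.3 / 4.5 |
| p<0.05 | 0.527 / 0.545 / 0.561 | 0.504 / 0.495 / 0.495 | 2.3 / 5.0 / 6.6 |
| p<0.05, features correlated 0.3 | 0.510 / 0.518 / 0.521 | 0.499 / 0.500 / 0.497 | 1.1 / 1.8 / 2.4 |

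The p<0.05 rule is lenient. A noise region passes with probability 1−0.95^7 = 0.30, so with 200 candidates about (200−21)×0.30 = 54 noise regions join the 21. That gives 75×7 = 525 local features beside 75×74/2 = 2,775 unscreened connectivity features, which dilute the effect.

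Under FDR with an assumed weak true effect (d=0.25 per group step in 5% of local measures; 100 data sets; 80 and 200 regions), local plus connectivity features give 0.558 versus 0.549 and 0.584 versus 0.568, or +0.9 and +1.6 points. Other feature weightings reach +3.0 (0.654 versus 0.624).

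As a control, a separate run with 35/15 training/test subjects per group and no added regions gave 0.499 either way, so the optimism comes from the selection. A second noise simulation gave about 0 points under FDR and about 4 points at p<0.05 with local plus connectivity features and 50 to 80 regions.

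**4. Kernel choice in C6b.** Assumed: 100 subjects, pure noise, 21×7+210 = 357 features, 4 kernels, 2 values of C, 200 splits at 70/30, 10 data sets. The average kernel scored 0.511 and the kernel best on the mean scored 0.519, a gain of 0.008, or about 1 point. This is a small run.

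**The case against.** The strongest reply is that the deciding material cannot be seen. Figure 3 is captioned for both aims, C6b ties its cross-validation to that figure, and C6 defers to a published method. Either may draw a common scheme with selection inside training. This stands, and it is why the conclusion is conditional. It does not clear the plan: a common split alone would not show where the region revision sits, and the text, followed in the order written, puts it first.

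The second reply is that the stated SA1 thresholds are strict: FDR in C4, and permutation methods in C7b and C7c. Under FDR the noise result is essentially zero. This also stands as to size, but none of these is given as the rule for revising the SVM regions, and C3c states no threshold for the task regressors.

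Some stronger readings are not supported:
- **A bias of about 15 points.** A reader might infer this from p<0.05 screening with 200 candidates and local features only. That drops the connectivity matrices that C6 lists. Giving the local and connectivity blocks equal weight yields about 14 points, but the plan does not state that weighting.
- **Noise alone would reach the 70% mark.** With local plus connectivity features at p<0.05, only 0 to 1% of noise data sets did. The mark is also a level of usefulness, not a success criterion.
- **Accuracy of 0.76 from kernel choice.** This is the best single run in the small simulation. Nothing in the plan says a best single run will be reported.
- **Equal harm to SA2b from the region revision.** The revision uses group, not relapse, so it leaks only so far as the two are related.

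**Conclusion.** The concern holds conditionally and should be fixed. C6 revises the regions by group separation and C6a predicts the same groups, with no readable limit to training subjects. If Figure 3 or the cited method does not supply that limit, SA2a accuracy will tend to be optimistic. The direction is firm; the size is open, because the candidate count, the threshold and the scaling of the features are unstated.

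Under the assumptions above, the optimism runs from about 0 points (FDR, noise), through 1 to 3 (FDR, weak true effect), to 2 to 7 (p<0.05, any of 7 measures, local plus connectivity features), or 1 to 2 in that last case if features correlate 0.3. The kernel choice in SA2b is a minor addition of about 1 point if kernels are compared on mean test accuracy.

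**What to change.** - Repeat all label-based region and feature selection inside each training set, for SA2a and SA2b. Alternatively, keep Table 3 fixed for the primary SVM result and label the expanded set exploratory.
- Choose kernel and parameters by the inner 10-fold cross-validation only, and use the outer 70/30 test sets only for scoring.
- Apply the same scheme to SA2a with splits stratified by group. Report the mean outer accuracy as pairwise balanced accuracy for the 6 classifiers or as mean recall over the four groups, because C6c defines balanced accuracy for two classes only.
- If Figure 3 already nests the selection, say so in the text of C6.

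The cost is SAP wording, more computing time and possibly a less favourable accuracy. No new data are needed. Fixing Table 3 for the primary result would move regions first found in SA1 to the exploratory analysis; nesting avoids that.
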